1.5. Randomization and Blinding

Randomization

Central randomization will be implemented in this study. Subjects will be randomly assigned to 1 of 2 treatment arms in a 1:1 ratio based on a computer-generated randomization schedule prepared before the study by or under the supervision of the sponsor. The randomization will be balanced by using randomly permuted blocks and will be stratified for NEWS2 (4-5 or >5) (NEWS

is changed to NEWS2 per CTP amendment 2) at screening, type of baseline SOC (including or not including influenza antiviral treatment), and time since onset of influenza symptoms (first administration of study drug ≤ 72 hours or between 72 and 96 hours since onset of influenza symptoms). The interactive web response system (IWRS) will assign a unique treatment code, which will dictate the treatment assignment and matching study drug kit for the subject. The requestor must use his or her own user identification and personal identification number when contacting the IWRS and will then give the relevant subject details to uniquely identify the subject.

Blinding

The investigator will not be provided with randomization codes. The codes will be maintained within the IWRS, which has the functionality to allow the investigator to break the blind for an individual subject.

Data that may potentially unblind the treatment assignment (ie, study drug plasma concentrations) will be handled with special care to ensure that the integrity of the blind is maintained and the potential for bias is minimized. This can include making special provisions, such as segregating the data in question from view by the investigators, clinical team, or others as appropriate until the time of database lock and unblinding.

Under normal circumstances, the blind should not be broken until all subjects have completed the study and the database is finalized. Otherwise, the blind should be broken only if specific emergency treatment/course of action would be dictated by knowing the treatment status of the subject. In such cases, the investigator may in an emergency determine the identity of the treatment by contacting the IWRS. It is recommended that the investigator contact the sponsor or its designee if possible to discuss the particular situation, before breaking the blind. Telephone contact with the sponsor or its designee will be available 24 hours per day, 7 days per week. In the event the blind is broken, the sponsor must be informed as soon as possible. The date, time, and reason for the unblinding must be documented by the IWRS, in the appropriate section of the electronic case report form (eCRF) and in the source documents. The documentation received from the IWRS indicating the code break must be retained with the subject's source documents in a secure manner.

[figure not shown]
2. GENERAL ANALYSIS DEFINITIONS

All analysis dataset preparations and statistical analyses will be performed using SAS[®] version 9.2 or higher.

2.1. Visit Windows, Phase Definitions and Baseline

The study is set up as shown in Figure 1. The phases will be constructed as shown in Table 1.

Figure 1: Study time line.

¹ A subject with extended treatment will be treated an extra 5 days compared to the subjects without extended treatment.

Note: Depending on the time of screening/enrollment, subjects will receive 1 dose (evening) or 2 doses (morning and evening) of study drug on Day 1. For subjects who receive only 1 dose of pimodivir or placebo on Day 1 (evening), dosing should continue until the morning of Day 6 so that all subjects receive 10 doses in total, or for subjects with extended treatment until the morning of Day 11, so all subjects with extended treatment receive 20 doses in total.

2.1.1. Phase Definitions

Table 1: Construction of phases

Trial phase	Trial subperiod ^{*1}	Start date	End date
Screening (phase 1)		The date of signing the informed consent with 00:00 as a timepart	1 minute before the first study drug intake
Treatment (phase 2)		Datetime of first study drug intake ^{*4}	Datetime of last study drug intake ^{*4} + 24 hours
	Planned Treatment (subperiod 1) ^{*2}	Datetime of first study drug intake ^{*4}	If extended treatment then Datetime of first study drug intake in extended treatment subperiod – 1 minute Else Datetime of last study drug intake ^{*4} + 24 hours
	Extended Treatment (subperiod 2) ^{*3}	Datetime of first study drug intake in extended treatment subperiod ^{*4}	Datetime of last study drug intake ^{*4} + 24 hours
Follow-up (phase 3)		End of the treatment phase +1 minute	Trial termination date (or date of last contact if later)

^{*1}: A treatment period will be constructed in the derived datasets with the same start and end date as the treatment phase.

^{*2}: The planned treatment subperiod will be present for all treated subjects.

^{*3}: The extended treatment subperiod will only be present for all subjects with extended treatment.

^{*4}: In case the time part of the study drug intake is missing the imputed time part will be used as described below.

Additionally, the treatment phase and follow-up phase will be combined in the analysis.

In case the time part of first study drug intake is missing the randomization time will be used. In case the time part of the randomization time is also missing we impute the time part with 8:00 if taken in the morning or with 20:00 if study drug was taken in the evening. In case the time of the last study drug intake is missing, the time part will be imputed with 8:00 if the last study drug was taken in the morning or with 20:00 if the last study drug was taken in the evening.

In case the time part of first intake of the treatment extension is missing, the time part will be imputed with 8:00 if the last study drug of the planned 5 days of treatment was taken in the morning or with 20:00 if the last study drug was taken in the evening.

The last phase, whichever it is for a subject, always ends on 23:59 of the day of trial termination (or date of last contact if later).

Assessments will be assigned to phases and subperiods based on their start datetime, but seconds will not be taken into account. If only one assessment is expected per day and the day part of the start date of the assessment is present but the time part is missing, the assessment will be treated as if it happened at 00:00 of the day of the assessment (except for Adverse Events see details in Section 7.1). No imputations on missing times/time parts will be made in the analysis datasets.

In case more than one assessment per day is expected and time part is missing:

1. Allocate according to the timepoint: Morning=00:00, Middle of the day=12:00, Evening=20:00
2. If 1 timepoint is missing on day x: Check the non-missing timepoints of the other records on this day x. Allocate this record to the timepoint of day x that is not already covered. Then apply 1.
3. If 2 timepoints are missing on day x: Check the non-missing timepoint of the other record on this day x. Allocate these records to the timepoints of day x that are not already covered, assigning the smallest XXSPID value to the earlier timepoint and the larger XXSPID value to the later timepoint. Then apply 1.
4. If 3 timepoints are missing on day x: allocate using the values of XXSPID, i.e. lowest number is morning, next is middle of the day, highest number is evening. Then apply 1.

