- a. Subjects who prematurely discontinue study drug treatment for any reason (except withdrawal of consent) will be asked to continue with their remaining study visits and assessment schedule. Subjects who withdraw consent during the treatment or follow-up phase will be offered an optional Safety Follow-up Visit. The optional Safety Follow-up Visit will occur the day of consent withdrawal or the day after and will consist of the same assessments as at the Final Study Visit (Day 33), with optional PRO completion.
- b. On Day 6, subjects will receive 1 dose (evening) or 2 doses (morning and evening) of study drug as part of the extension phase. For subjects who receive only 1 dose of pimodivir or placebo on Day 6 (evening), dosing should continue until the morning of Day 11 so that the subject receives 10 doses in total during the extension phase.
- c. Central virology testing: Nasal MT swabs should be obtained from the left and the right nostrils (from both nostrils if feasible, but from only one nostril otherwise) and pooled into the same collection tube. In case the subject is intubated, endotracheal samples should be taken as well, at the same time as the nasal MT swab. Samples will be collected on Days 6, 7, 8, 9, 10, 14, and 19. Sampling should be done at approximately the same time (± 4 hours) on each sampling day. Leftovers from nasal swabs and endotracheal samples collected for virology testing may be used for protein biomarker analysis, if not restricted by local regulations.
- d. Vital signs include body temperature, pulse rate, respiratory rate, and blood pressure. For peripheral capillary oxygen saturation, it should be recorded whether the measurement was with or without supplemental oxygen.
- e. Vital signs/peripheral capillary oxygen saturation (pulse oximetry)/ACVPU are to be evaluated 3 times daily: in the morning (prior to study drug intake if applicable), approximately half-way in the middle of the day, and in the evening (prior to study drug intake if applicable).
- f. Subjects should rest in a supine position for at least 5 minutes before ECG collection and should refrain from talking or moving arms or legs. If blood sampling or vital signs measurement is scheduled for the same time point as ECG recording, the procedures should be performed in the following order: ECGs, vital signs, blood draw.
- g. Questionnaire (Return to daily activities) to be completed once daily onto the ePRO device.

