6. DOSAGE AND ADMINISTRATION

During the treatment period, all subjects will receive study drug in a 1:1 ratio in 1 of the 2 treatment arms shown in the table below. Depending on the time of screening/enrollment, subjects will receive 1 dose (evening) or 2 doses (morning and evening) of study drug on Day 1. Subjects may delay or bring forward administration of the second dose (by no more than 4 hours) only if the nominal timing for this second dose falls in the middle of the night. For subjects who receive only 1 dose of pimodivir or placebo on Day 1 (evening), dosing should continue until the morning of Day 6 so that all subjects receive 10 doses in total.

Subjects who are eligible for the blinded extension arm will receive study drug as described in the table below. Subjects will receive 1 dose (evening) or 2 doses (morning and evening) of study drug on Day 6. For subjects who receive the first dose of study drug in the second treatment course in the evening of Day 6, dosing should continue until the morning of Day 11 so that the subject receives 10 doses in total during the second treatment course.

Study-site personnel will instruct subjects on how to store study drug for at-home use as indicated for this protocol.

No post-study medication is provided as part of this protocol.

	Treatment Arm 1	Treatment Arm 2	Treatment Extension Arm 1^a	Treatment Extension Arm 2^a
Test Article(s)	Pimodivir (Day 1 through Day 5) + SOC treatment ^{b,c}	Placebo (Day 1 through Day 5) + SOC treatment ^{b,c}	Pimodivir (Day 6 through Day 10) + SOC treatment ^{b,c}	Placebo (Day 6 through Day 10) + SOC treatment ^{b,c}
Description	300 mg tablet	Placebo tablet	300 mg tablet	Placebo tablet
Dose per Delivery	Day 1 to Day 5 600 mg pimodivir (2 tablets)	Day 1 to Day 5 Placebo (2 tablets)	Day 6 to Day 10 600 mg pimodivir (2 tablets)	Day 6 to Day 10 Placebo (2 tablets)
Frequency	Bid	Bid	Bid	Bid
Total Daily Dose	1,200 mg	NAP	1,200 mg	NAP
Delivery Method^d	Oral	Oral	Oral	Oral
Food/Fasting Requirement	No food requirements	No food requirements	No food requirements	No food requirements

Abbreviations: bid: twice daily; NAP: not applicable; SOC: standard-of-care.

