9.1.3. Double-blind Treatment Phase

Subjects who meet all eligibility criteria will be randomized in a 1:1 ratio to receive 1 of the following 2 treatments:

- Pimodivir 600 mg bid on Days 1 through 5 + SOC treatment; OR
- Pimodivir placebo bid on Days 1 through 5 + SOC treatment.

For subjects who receive only 1 dose of pimodivir or placebo on Day 1 (evening), dosing should continue until the morning of Day 6 so that all subjects receive 10 doses in total.

The SOC treatment is determined by the investigator based on local practice, and may include influenza antivirals and/or supportive care only. The choice to use influenza antivirals as part of the SOC should be made before randomization. The influenza antiviral should be started no later than the day of first study drug intake. An influenza antiviral as part of the SOC cannot be changed (eg, switching one influenza antiviral for another) during either the treatment period or extension phase, with the exception that an influenza antiviral may be discontinued in the case of a suspected AE.

Subjects will undergo sparse PK sampling for the measurement of plasma concentrations of pimodivir at the time points specified in the [TIME AND EVENTS SCHEDULES](#).

Throughout the treatment period, PRO assessments will be completed before any other assessments for a specific visit. At the time points specified in the [TIME AND EVENTS SCHEDULES](#), a symptom-directed physical examination, blood sampling (for hematology, chemistry, drug concentrations, and biomarker [if not restricted by local regulations] analysis), urine sampling (for urinalysis), and a pregnancy test (urine or serum for females of childbearing potential) will be performed; nasal MT swabs will be obtained for central virology testing; and vital signs, peripheral capillary oxygen saturation, and level of consciousness (ACVPU) will be measured. If subjects are intubated, an endotracheal sample should be collected at the same time points as the nasal MT swab. A taste and swallowability questionnaire will be completed by adolescent subjects, within approximately 15 minutes after the first and last intake of the pimodivir or placebo tablet (not applicable when tablets are administered via nasogastric tube).

Subjects will be observed/interviewed for any AEs, concomitant medication will be reviewed, and AEs and concomitant medication will be recorded.

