Once daily, an assessment of readiness for discharge and ICU level of care requirement will be performed.

Subjects, who are discharged during the treatment phase, will receive study drug for at-home use.

End of Treatment

A subject will be considered to have completed treatment after 5-day therapy of pimodivir or placebo (ie, 10 doses).

Subjects (1) who complete the 5-day treatment, (2) who are still hospitalized upon treatment completion, (3) who are on invasive mechanical ventilation or who have an ongoing respiratory deficiency as evidenced by having an SpO₂ <94% on room air, or in case of known pre-influenza SpO₂ <94% (eg, due to COPD), the current blood oxygen saturation on room air is lower than pre-influenza infection levels by at least 3%, (4) who, in the opinion of the investigator, are expected to derive clinical benefit from extending the treatment period, and (5) for whom the investigator agrees to extend treatment with the same SOC will be given the option for treatment extension. In the second blinded course of treatment, subjects will continue treatment with pimodivir or placebo for another 5 days in combination with continued SOC treatment. If the SOC contained no influenza antiviral during the first treatment period, no influenza antiviral can be started in the treatment extension as part of the SOC (see Section 9.1.4).

Early Withdrawal

Subjects who prematurely discontinue study drug treatment for any reason (except withdrawal of consent) will be asked to continue with their remaining study visits and assessment schedule. Subjects who withdraw consent during the treatment phase will be offered an optional Safety Follow-up Visit. The optional Safety Follow-up Visit will occur the day of consent withdrawal or the day after and will consist of the same assessments as at the Final Study Visit (Day 28 or Day 33), with optional PRO completion. If the subject discontinues treatment due to an AE or other medical reason, efforts will be made by the investigator to continue following up with the subject at regular intervals until the AE normalizes or returns to the subject's baseline condition. The sponsor and the investigator will agree on an acceptable individual follow-up schedule for these subjects.

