4.4. Extent of Exposure

The extent of exposure (hours) is defined as datetime of last study drug intake – datetime of first study drug intake + 12 hours. Note: treatment interruptions will not be taken into account.

Extent of exposure will be summarized descriptively in the treatment phase, overall and by treatment subperiod.

A listing will be made to present the exposure to study drug for subjects impacted by COVID-19 (based on reason ‘Other’ containing ‘COVID’).

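### With no recorded time for the first extension dose, SAP 2.1.1 imputes the wrong half of the day under uninterrupted twice-daily dosing, misplacing the planned/extended boundary by a nominal 12 hours

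*SAP*

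**What the plan says.** SAP 2.1.1 (Phase Definitions) sets out how missing intake times are filled. For the very first intake, the randomization time is the first fallback; failing that, "we impute the time part with 8:00 if taken in the morning or with 20:00 if study drug was taken in the evening". The last intake is handled in the same way, from its own half-day. The first extension intake is handled differently. Its time is "imputed with 8:00 if the last study drug of the planned 5 days of treatment was taken in the morning or with 20:00" (the later value after an evening dose), so the half-day comes from the preceding dose.

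Table 1 in the same section uses this datetime twice: it starts the extended treatment subperiod and, less one minute, ends the planned one.

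The dosing pattern is given elsewhere:
- Protocol 9.1.3 specifies twice-daily dosing and counts the planned course as 10 doses.
- Protocol 6: "For subjects who receive only 1 dose of pimodivir or placebo on Day 1 (evening), dosing should continue until the morning of Day 6".
- Footnote b of Time and Events Schedule 3: "On Day 6, subjects will receive 1 dose (evening) or 2 doses (morning and evening) of study drug as part of the extension phase".
- Protocol 6, for an evening start of the second course: "For subjects who receive the first dose of study drug in the second treatment course in the evening of Day 6, dosing should continue", with Day 11 morning as its end, making 10 extension doses.
- The note under Figure 1 in SAP 2.1 gives an evening starter with extension 20 doses, ending on the morning of Day 11.

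**The concern.** Consecutive twice-daily doses alternate between morning and evening. A rule that copies the half-day of the preceding dose cannot locate the next one unless a dose slot is skipped. Here it sets the start of the second course.

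The consequence is misallocation between subperiods. SAP 2.1.1 assigns assessments to subperiods by start datetime, and SAP 7.1.1 does the same for adverse events. SAP 7.1.2 tabulates adverse events by subperiod, and SAP 7.2.1 and 7.3.1 derive worst laboratory and vital-sign abnormalities by subperiod. For exposure, SAP 4.4 states: "Extent of exposure will be summarized descriptively in the treatment phase, overall and by treatment subperiod". A boundary misplaced by half a day moves Day 6 data from one column to the other in these tables.

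**Working it through.** **Inputs.** Morning dose = 08:00 and evening dose = 20:00 (SAP 2.1.1). Nominal interval 12 h (twice daily, Protocol 9.1.3). Ten planned and ten extension doses (Protocol 6 and 9.1.3).

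**Formula.** Dose k falls at the time of dose 1 + 12 h × (k − 1).

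**Reproducing the SAP's own figure.** For an evening Day 1 start, dose 10 is 9 × 12 = 108 h after Day 1 20:00, which is Day 6 08:00. Dose 20 is 19 × 12 = 228 h after it, which is Day 11 08:00. Both match the note under Figure 1 in SAP 2.1 (10 doses by the morning of Day 6, 20 by the morning of Day 11). For a morning start, the same formula gives dose 10 on Day 5 at 20:00 and dose 20 on Day 10 at 20:00, consistent with the Day 6 to Day 10 extension in Protocol 6.

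**Applying the imputation rule to dose 11, on Day 6.**

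| Day 1 start | Dose 10 | Dose 11, nominal | Dose 11, SAP rule | Error | Dose 11, values swapped |
|---|---|---|---|---|---|
| Morning | Day 5 20:00 | Day 6 08:00 | Day 6 20:00 | +12 h (late) | Day 6 08:00, error 0 |
| Evening | Day 6 08:00 | Day 6 20:00 | Day 6 08:00 | −12 h (early) | Day 6 20:00, error 0 |

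For the evening starter, the imputed time is the slot of dose 10 itself. The planned subperiod then closes at 07:59, one minute before its own nominal last dose.

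**Effect on allocation.** For the morning starter, data timed on Day 6 from 08:00 until just before 20:00 go to planned instead of extended treatment. For the evening starter, they go to extended instead of planned. Midday vital signs are the clearest case. Schedule 3 requires vital signs three times a day from Day 6, and SAP 2.1.1 sets a midday reading with no clock time to 12:00, inside the window.

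**Effect on extension exposure, if the imputed time is used in SAP 4.4** (last intake − first intake + 12 h, full course):
- Morning starter, nominal: Day 6 08:00 to Day 10 20:00 = 108 h; 108 + 12 = 120 h.
- Morning starter, SAP rule: Day 6 20:00 to Day 10 20:00 = 96 h; 96 + 12 = 108 h (12/120 = 10% too low).
- Evening starter, nominal: Day 6 20:00 to Day 11 08:00 = 108 h; 108 + 12 = 120 h.
- Evening starter, SAP rule: Day 6 08:00 to Day 11 08:00 = 120 h; 120 + 12 = 132 h (10% too high).

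**Length of the extended subperiod in Table 1** (first extension intake to last intake + 24 h): nominally 108 + 24 = 132 h. Under the rule it is 96 + 24 = 120 h for a morning starter and 120 + 24 = 144 h for an evening starter.

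**Sensitivity.** Protocol 6 lets a dose move by up to 4 h when its nominal time falls in the middle of the night. A single shift of that size would make the error 8 to 16 h.

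**Alternative reading.** In the evening branch, the last study drug could be taken to mean the last extension dose. A 10-dose twice-daily course begins and ends in opposite halves of the day, so the errors are again +12 h and −12 h.

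**The case against.** The strongest reply is that the rule is not wrong in every case. Protocol 6 allows one or two extension doses on Day 6 and does not expressly tie the choice to when dose 10 was taken. Eligibility for extension is assessed on completion of the planned course (Protocol 9.1.4) and depends on oxygen saturation and investigator judgement (Protocol 4.3). A subject who finishes on Day 5 evening and first takes extension drug on Day 6 evening gets the correct imputed time, and a skipped final planned dose can have the same effect. This stands. A reader might infer that every imputed start is wrong, but the documents support that only for uninterrupted dosing. A bare swap would be wrong in the exceptions, so the fix needs a clause for them.

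The reach is also limited, and these points stand too:
- Schedule 3 has no Day 6 laboratory draw (the next is Day 8), so only unscheduled laboratory results could move.
- Adverse events without an onset time are allocated on partial information and may be counted in several subperiods (SAP 7.1.1). Only those with a recorded time in the window move.
- Vital-sign summaries by timepoint do not depend on the boundary; only the outputs by subperiod do.
- SAP 4.4 does not say that the imputed times feed exposure. On a plain reading, planned-subperiod exposure uses planned intakes only. A reader might infer that exposure in both subperiods is wrong, but only the extension figure is at risk, and conditionally.
- Compliance by subperiod uses the extension start date, not its time (SAP 4.3).
- Extension subjects are inpatients when the decision is made, and Protocol 7 provides for recording intake dates and times, so missing times may be few.

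**Conclusion.** The point holds for subjects on uninterrupted twice-daily dosing whose first extension intake has no recorded time. For them, the rule contradicts the protocol's dosing schedule and the SAP's own note under Figure 1, and no reading found in the documents reconciles them. The imputed start is nominally 12 h early after a morning last planned dose and 12 h late after an evening one. Subperiod allocation of timed Day 6 data between about 08:00 and 20:00 is wrong as a result. The 10% change in extension exposure rests on the further assumption that these times are used in SAP 4.4.

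The number of subjects affected cannot be derived from the documents. A reader might infer bias between arms or an effect on the main efficacy result. The documents support neither: the rule is the same in both arms, its errors run in opposite directions for the two dosing patterns, and the Day 6 primary endpoint, the testing hierarchy, the overall treatment phase, the combined treatment-plus-follow-up tables and total exposure do not use this boundary. It is a definite but narrow data-handling error.

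**What to change.** In SAP 2.1.1, swap the two values for a missing time of the first extension intake: 20:00 if the last planned dose was taken in the morning, 8:00 if it was taken in the evening. Add an exception: where the records show that the first extension dose was taken in a different half of the day, use that half-day (8:00 for morning, 20:00 for evening), as the SAP already does for the first and last intakes. It would also help to state in SAP 4.4 whether imputed intake times enter the exposure calculation.

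The cost is a sentence or two in the SAP and a correspondingly small change in the phase-derivation code. No new data are needed, and no dosing instruction changes.
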